The empirical estimate for the prevalence of ATTR-CM in HFpEF participants is approximately 10%. The study will enroll approximately 2000 HFpEF participants within whom it is expected to detect 200 ATTR-CM participants. Enrollment will be stopped if 200 ATTR-CM participants are identified before 2000 HFpEF are enrolled. No formal sample size calculation was performed. A sample size of 2000 HFpEF participants would be sufficient to inform treatment guidelines and yield an estimate for the global prevalence of ATTR-CM in HFpEF participants with a precision of $\pm 2.5\%$.

Statistical Methods

The primary endpoint is an estimate of the global prevalence of ATTR-CM in HFpEF participants. Diagnosis of ATTR-CM is defined as:

- Cardiac Scintigraphy Grade 1, with confirmation of ATTR by cardiac biopsy; or
- Cardiac Scintigraphy Grade 2 or above.

This global prevalence estimate will be obtained by dividing the number of participants who are diagnosed with ATTR-CM in the study by the total number of HFpEF participants evaluated. A 95% confidence interval on the estimate will also be calculated.

As secondary analysis, prevalence will be estimated for:

- Regions and countries;
- Age categories (60-64, 65-69, 70-74, 75-79, 80-85, >85);

- Gender (male, female).

Prevalence estimates along with 95% confidence interval (CI) will be generated for regions and countries with at least 50 participants. For regions and countries that enroll fewer than 50 participants, prevalence will not be estimated. Regions will be defined in the statistical analysis plan. The proportion of HFpEF participants who were diagnosed with wild-type and variant ATTR-CM will be descriptively summarized.

As a general rule, the secondary endpoints other than the prevalence estimates and all CCI [REDACTED] reported as numerical values will be analyzed descriptively using mean, standard deviation, median, minimum, and maximum. Endpoints that are categorical will be summarized using frequency tables.

Analysis by Scintigraphy:

Participants who are diagnosed with ATTR-CM will be analyzed by scintigraphy grades (Grade 1, 2, or 3) using the 6-MWT, NT-proBNP, medical history, demographics (including age, TTR Genotype, gender and race), NYHA classification (Class I, II, III, or IV), and all CCI [REDACTED]

Analysis by Disease Status:

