a Val122Ile mutation and 46 months for patients with ATTR-CM due to wild-type TTR,¹⁷ with most patients dying from cardiac causes, including sudden death, CHF, and myocardial infarction.^{18,19} Untreated ATTR-CM is currently associated with mean progression to death within 24 to 36 months (median survival 25.6 months) of diagnosis for variants and up to 60 months (median survival 43.0 months) for wild type.²⁰

The prevalence of ATTR-CM is defined as rare, but no prevalence estimates have been published. There are more than 120 mutations in the TTR gene which cause a variable phenotype determined by the relative extent of amyloid deposition in the myocardium and peripheral nerves.²¹ Though prevalence of wild-type TTR is uncertain, studies using a non-biopsy approach to diagnosis^{22,23} report a prevalence of 13% in HF patients with preserved ejection fraction,²⁴ 16% in patients undergoing transcatheter aortic valve replacement for severe aortic stenosis,²⁵ and 5% of patients with presumed hypertrophic cardiomyopathy.²⁶

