9. STATISTICAL CONSIDERATIONS

Detailed methodology for summary and statistical analyses of the data collected in this study will be documented and will be maintained by the sponsor.

The primary completion date (PCD) for the global prevalence estimate will be the date when all enrolled participants have either been diagnosed with ATTR-CM (scintigraphy grades 2 or 3), have scintigraphy grade 1 or found to be negative for ATTR-CM (scintigraphy grade 0) and have completed Follow-up Visit 1. Results will be reported after PCD and at the end of study (LPLV for participants with scintigraphy grade 1, 2 or 3).

The empirical estimate for the prevalence of ATTR-CM in HFpEF participants is approximately 10%. The study will enroll approximately 2000 HFpEF participants within whom it is expected to detect 200 ATTR-CM participants. Enrollment will be stopped if 200 ATTR-CM participants are identified before 2000 HFpEF are enrolled. No formal sample size calculation was performed. A sample size of 2000 HFpEF participants would be sufficient to inform treatment guidelines and yield an estimate for the global prevalence of ATTR-CM in HFpEF participants with a precision of $\pm 2.5\%$.

The primary endpoint is an estimate of the global prevalence of ATTR-CM in HFpEF participants. Diagnosis of ATTR-CM is defined as:

- Cardiac Scintigraphy Grade 1, with confirmation of ATTR by cardiac biopsy; or
- Cardiac Scintigraphy Grade 2 or above.

This global prevalence estimate will be obtained by dividing the number of participants who are diagnosed with ATTR-CM in the study by the total number of HFpEF participants evaluated. A 95% confidence interval on the estimate will also be calculated.

As secondary analysis, prevalence will be estimated for:

- Regions and countries.
- Age categories (60-64, 65-69, 70-74, 75-79, 80-85, >85).
- Gender (male, female).

Prevalence estimates along with 95% CI will be generated for regions and countries with at least 50 participants. For regions and countries that enroll fewer than 50 participants, prevalence will not be estimated. Regions will be defined in the statistical analysis plan. The proportion of HFpEF participants who were diagnosed with wild-type and variant ATTR-CM will be descriptively summarized.

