5.2. General Methods

5.2.1. Analyses for Prevalence Endpoints

The primary endpoint estimating prevalence will be evaluated by dividing the number of participants who are classified as ATTR-CM positive by Cardiac Scintigraphy as defined in [Section 3.1](#) by the total number of evaluable participants. The secondary endpoints estimating prevalence will be evaluated by dividing the number of participants who are classified as ATTR-CM positive by Cardiac Scintigraphy as defined in [Section 6.1.1.1](#) by the total number of HFpEF evaluable participants in the study (primary) or the relevant subgroup (secondary). Exact 95% confidence intervals for the prevalence estimates will be calculated using the method of Clopper and Pearson.¹

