6. ANALYSES AND SUMMARIES

6.1. Primary Endpoint(s)

The primary endpoint is an estimate of the global prevalence of ATTR-CM in HFpEF participants. Diagnosis of ATTR-CM is defined as:

- Cardiac Scintigraphy Grade 1, with confirmation of ATTR by cardiac biopsy during the study period, or:
- Cardiac Scintigraphy Grade 2 or above.

The primary endpoint will be evaluated by dividing the number of participants who are classified as ATTR-CM positive by Cardiac Scintigraphy (as noted above) by the total number of HFpEF evaluable participants in the study. The proportion of Scintigraphy Grade 1 participants that are diagnosed with ATTR-CM will be estimated. Scintigraphy

Grade 1 participants that are diagnosed with ATTR-CM using a criteria other than cardiac biopsy and participants lost to follow-up without a confirmation of cardiac biopsy will be assumed as not diagnosed with ATTR-CM in the primary analysis. Exact 95% confidence intervals for the prevalence will be calculated using the method of Clopper and Pearson.¹ The primary analysis will be generated using the “Evaluable Analysis Set”.

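### The stated ±2.5% precision has no derivation and does not follow from 2000 participants at 10% prevalence; the planned exact 95% interval is 8.7% to 11.4%, about ±1.3 points

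*Protocol*

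**What the plan says.** Protocol 9 (Statistical Considerations) starts from "The empirical estimate for the prevalence of ATTR-CM in HFpEF participants is approximately 10" per cent, plans about 2000 participants, and expects 200 cases among them. It then says "No formal sample size calculation was performed". The next sentence nevertheless gives a number: 2000 participants are expected to "yield an estimate for the global prevalence of ATTR-CM in HFpEF participants with a precision of $\pm 2.5" per cent. The Synopsis (Protocol 1.1, Number of Participants) makes the same claim: "A sample size of 2000 HFpEF participants would be sufficient to inform treatment guidelines and yield an estimate for the global prevalence", with the same ±2.5%.

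Three other statements bear on the figure:

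- Protocol 9 has an early-stop rule: "Enrollment will be stopped if 200 ATTR-CM participants are identified before 2000 HFpEF are enrolled".
- Protocol 2.2 cites studies that "report a prevalence of 13% in HF patients with preserved ejection fraction", which is higher than the planning value.
- SAP 6.1 fixes the interval for the primary endpoint: "Exact 95% confidence intervals for the prevalence will be calculated using the method of Clopper and Pearson". SAP 5.2.1 says the same for prevalence estimates generally.

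Neither document gives a confidence level, method, design effect or other allowance behind ±2.5%.

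**The concern.** SAP 5.1 plans no formal hypothesis test, so the case for the sample size rests on precision, and ±2.5% is the only precision figure given for the primary endpoint. It should therefore follow from the planned number, the assumed prevalence and the planned interval method. A quick normal approximation at 10% and 2000 gives about ±1.3 points, roughly half the stated value.

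What is at stake is the reader's understanding of the design. Someone who compares the reported interval with the plan will see a mismatch that neither document explains, and cannot tell what precision was intended. No participant's data and no analysis depend on the figure.

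**Working it through.** **Inputs.** Prevalence 10%, N = 2000 and 200 expected cases (Protocol 9). Exact 95% Clopper-Pearson interval (SAP 5.2.1 and 6.1), taken as two-sided. All 2000 are treated as evaluable and independent, which is the simplest reading.

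**Attempt to reproduce ±2.5%.** With x cases among n participants, the exact limits are beta quantiles:

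- lower = Beta(0.025; x, n − x + 1)
- upper = Beta(0.975; x + 1, n − x)

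For x = 200 and n = 2000 the interval is 8.72% to 11.40%. The arms are −1.28 and +1.40 points, the full width is 2.68, and the half-width is 2.68/2 = 1.34. As a check, the normal approximation gives 1.96 × √(0.10 × 0.90/2000) = 1.31 points. The stated figure is 2.5/1.34 ≈ 1.9 times the planned one.

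**Other readings tried.**

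| Reading | Result (points) |
|---|---|
| 99% exact interval, 200/2000 | ±1.75 |
| 99.9% exact interval, 200/2000 | ±2.23 |
| Worst case at N = 2000 (50% prevalence), exact 95% | ±2.2 |
| Full width of the exact 95% interval, 200/2000 | 2.68 |
| Full width, normal approximation | 2.63 |

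None gives 2.5. The worst-case row is the most telling: the half-width cannot reach 2.5 points at N = 2000 under the planned method, whatever the prevalence.

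If ±2.5% is read as relative precision (±0.25 points at 10%), the number needed is 1.96² × 0.09/0.0025², about 55,300.

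**Working backwards.** At 10%, the normal approximation needs 1.96² × 0.09/0.025² = 553.2, so 554 participants, for ±2.5 points. The exact half-width is 2.505 at 59/590 and 2.483 at 60/600. To reach ±2.5 points with 2000 participants, the design effect would have to be (2.5/1.315)² ≈ 3.6. No design effect is stated.

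**Precision in the other settings the protocol raises** (exact 95%):

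| Setting | N | Interval | Half-width (points) |
|---|---|---|---|
| 13% prevalence, full enrolment (260 cases) | 2000 | 11.6% to 14.6% | 1.50 |
| 13% prevalence, stop at 200 cases | 1538 | 11.4% to 14.8% | 1.71 |
| 20% prevalence (assumed), stop at 200 cases | 1000 | 17.6% to 22.6% | 2.53 |

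The early-stop rows use N = 200/prevalence and treat N as fixed. That is an approximation, because the rule stops on the case count. The last row is the only one near 2.5, and it uses neither the 10% nor the 2000 on which the protocol's planning rests.

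**Evaluable participants.** The SAP denominator excludes non-evaluable scans (SAP 4), and the documents do not say how many to expect. If 5% to 25% were non-evaluable (an assumed range; N = 1900 to 1500), the half-width at 10% would be 1.38 to 1.55 points.

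**The case against.** The best defence is that ±2.5% was meant as a ceiling. The precision sentence conditions only on 2000 participants; the 10% stands in a separate sentence about expected cases. Read as a bound, ±2.5 points holds at every prevalence, since the maximum is 2.2. The reasons given for the reduction to 2000 speak of the number being adequate to meet or maintain the precision, which suggests a threshold. And because the protocol disclaims a formal calculation, one can argue that the fault is an unstated basis rather than an arithmetic error.

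Part of this stands. The bound reading is possible, and under it the design is comfortably adequate. But the text says that 2000 participants yield this precision; it does not say at most or within. The sentence sits beside the 10%, the 200 expected cases and the planned 95% interval, and the figure follows from none of them. Disclaiming a calculation explains why no derivation is shown, but does not support the number that follows.

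Two cautions about the replacement figure also stand. The ±1.3 points assumes that all 2000 are evaluable and that participants are independent, in a multi-center study. Any restated sentence must carry both conditions.

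**Conclusion.** The concern holds, as a minor point. From the plan's own inputs and interval method, the expected precision is 8.7% to 11.4%, or ±1.34 points, against a stated ±2.5. No 95% reading of a 2000-participant design gives the stated value. It could be a loose upper bound, an approximate full width, an allowance for stopping at 200 cases, or an unstated design effect; the documents say none of these.

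Assuming independent participants, the error is conservative at both prevalences in the protocol, 10% and 13%. It does not show that the sample is too small. The primary estimate and its interval are unaffected.

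**What to change.** In Protocol 1.1 and 9, replace the ±2.5% clause with a sentence such as: *With 2000 evaluable participants and a prevalence of 10%, the exact 95% confidence interval is 8.7% to 11.4% (about ±1.3 percentage points), assuming independent participants.*

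Alternatively, keep ±2.5% and state its confidence level, its method and the assumption that produces it: an upper bound, a full width, an early-stop allowance or a design effect.

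In either case, add one line on precision if enrolment stops at 200 cases, treating N as fixed: about ±1.7 points at 13% prevalence (N = 1538) and about ±2.5 at an assumed 20% (N = 1000).

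The cost is one sentence in two places plus one added line. Sample size, primary estimate and interval method stay as they are. The drawback is that the narrower figure depends on evaluability and independence, so those conditions must stay in the sentence.

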1.4. Schedule of Activities (SoA)

The SoA table provides an overview of the protocol visits and procedures. Refer to the [Section 8](#) of the protocol for detailed information on each procedure and assessment required for compliance with the protocol.

The investigator may schedule visits (unplanned visits) in addition to those listed in the SoA table, in order to conduct evaluations or assessments required to protect the well-being of the participant.

Visit Identifier	Screening ^b	Visit 1 ^b	Follow-up 1 ^{bc}	Follow-up 2 ^{bf}
Visit Day		Day 1	14 Days Post Last Study Visit	6 Months Post Last Study Visit
Visit Window	Days -28 to -3		+10 Days	±30 Days
Informed consent	X			
Review entrance criteria	X			
Echocardiography ^a	X			
Medical History	X			
Record current medications		X		X
Demography	X			
NYHA classification		X		
Physical Examination including height and body weight	X			
Vital Signs	X			
CCI				
Scintigraphy		X		
TTR genotyping ^c		X		
CCI				
Laboratory samples				
Cardiac Biomarkers (NT-proBNP)		X		
Serum/Urine tests for primary (light chain) amyloidosis ^c		X		
Blood and Urine specimens for ATTR-CM biomarkers		X		
CCI				
Inform participant of diagnosis			X	
Adverse Event reporting	X	X	X	
Vital Status				X
Subsequent diagnosis testing				X

Abbreviations: NYHA = New York Heart Association; CCI
 CCI TTR – transthyretin; CCI
 CCI nal

- a. Echo performed if previous echo was ≥6 months prior to screening visit. If echo was performed within 6 months prior to screening and results are available, the echo can be used for study and does not need to be repeated.
- b. May be performed by remote participant visit.
- c. Participants should be followed for 14 days after the last study visit day to collect any AE/RRi information.
- d. Or at early discontinuation.

- e. Sample collected from all participants, only those samples from participants that are scintigraphy Grade 1, 2, or 3 will be analyzed.
- f. For participants with scintigraphy grade 1, 2 or 3.

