8.2.5. TTR Genotyping

Participants will require collection of a 4 mL blood sample for potential TTR genotype testing, subject to local laws and regulations, at Visit 1. If the participant is diagnosed with scintigraphy grades 1, 2, or 3 then the sample will be sent to a reference laboratory for analysis and complete genomic sequencing of the TTR gene.

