As a general rule, the secondary endpoints other than the prevalence estimates and all CCI reported as numerical values will be analyzed descriptively using mean, standard deviation, median, minimum and maximum. Endpoints that are categorical will be summarized using frequency tables.

Analysis by Scintigraphy:

Participants who are diagnosed with ATTR-CM will be analyzed by scintigraphy grades (Grade 1, 2, or 3) using the 6-MWT, NT-proBNP, medical history, demographics (including age, TTR Genotype, gender and race), NYHA classification (Class I, II, III, or IV), and all CCI

Analysis by Disease Status:

Participants who are diagnosed with ATTR-CM will be analyzed by NYHA Classification (Class I, II, III, or IV) using the 6-MWT, NT-proBNP, medical history, demographics (including age, TTR Genotype, gender, and race) CCI

Participants who are diagnosed with ATTR-CM will also be analyzed by 6-MWT quartile groups using NYHA baseline classification (Class I, II, III, or IV), NT-proBNP, medical history, demographics (including age, TTR Genotype, gender, and race) CCI

Analysis Comparing ATTR-CM participants with HFpEF patients without ATTR-CM:

HFpEF participants diagnosed with ATTR-CM will be compared with HFpEF participants not diagnosed with ATTR-CM descriptively using medical history, demographics (including age, TTR Genotype, gender, and race) CCI

Medical history data will be used to generate descriptive statistics for time from symptom onset to HFpEF diagnosis and time from symptom onset to ATTR-CM diagnosis.

Endpoints measuring proportion of participants (NYHA Classification and symptoms of interest from medical history) will be compared between HFpEF participants diagnosed with ATTR-CM and those that are not diagnosed with ATTR-CM. The Chi-square test will be used to compare the proportions between these 2 groups of HFpEF participants. Fisher's exact test will be used instead of the chi-square test if any one of the cells has ≤ 5 participants. Secondary CCI endpoints that are normally distributed will be compared between 2 groups of HFpEF participants using a t-test. Endpoints that are not normally distributed will be compared using the Wilcoxon rank sum test.

Safety Analysis:

Adverse events (AEs) and research related injuries (RRI) collected at Visit 1 or during Follow-up visits, will be summarized overall and separately for HFpEF participants diagnosed with ATTR-CM and HFpEF participants not diagnosed with ATTR-CM.

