9. APPENDICES

Appendix 1. Summary of Primary, Secondary, CCI ██████████ Analyses

Endpoint	Analysis Set	ATTR-CM vs HFpEF Participants	Analysis of ATTR-CM Participants by		Analysis
			Scintigraphy Grade	NYHA Baseline Classification	
Primary					
Global prevalence of ATTR-CM among participants with HFpEF.	Evaluable	N/A	N/A	N/A	Prevalence
Sensitivity/Supplementary Analysis					
Global prevalence of ATTR-CM as defined in Section 6.1.1.1 among participants with HFpEF will be estimated using the diagnosis criteria described in the primary endpoint, but will include all participants with Scintigraphy Grade 1 diagnosed with ATTR CM in the study (regardless of the cardiac biopsy).	Evaluable	N/A	N/A	N/A	Prevalence
Prevalence of ATTR-CM as defined in Section 6.1.1.1 among participants with HFpEF (regardless of the cardiac biopsy) in sub-groups (regions, age categories, gender).	Evaluable	N/A	N/A	N/A	Prevalence
Secondary					
Prevalence of ATTR-CM as defined in Section 6.1.1.1 among participants with HFpEF in sub-groups (regions, age categories, gender).	Evaluable	N/A	N/A	N/A	Prevalence
Proportion of participants with WT and hereditary forms among participants diagnosed with ATTR-CM as defined in Section 6.1.1.1 .	All Enrolled	✓	✓	✓	Proportion

New York Heart Association (NYHA) classification.	All Enrolled	✓	✓	N/A	Proportion
NTproBNP.	All Enrolled	✓	✓	✓	Descriptive Mean

CCI

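### TTR genotype is listed for comparison between participants with and without ATTR-CM, yet the only non-cases with a genotype would be unconfirmed Grade 1 participants

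*Protocol*

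**What the plan says.** **The comparison.** Protocol 9, under the analysis comparing ATTR-CM participants with HFpEF patients without ATTR-CM, sets cases against "HFpEF participants not diagnosed with ATTR-CM descriptively using medical history, demographics (including age, TTR Genotype, gender, and race"). The synopsis (1.1) repeats it.

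**Who is genotyped.** Footnote e to the Schedule of Activities, attached to TTR genotyping, reads "Sample collected from all participants, only those samples from participants that are scintigraphy Grade 1, 2, or 3 will be analyzed". Protocol 8.2.5 agrees: "If the participant is diagnosed with scintigraphy grades 1, 2, or 3 then the sample will be sent to a reference laboratory for analysis".

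**Who is a case.** Protocol 9 gives two routes: "Cardiac Scintigraphy Grade 1, with confirmation of ATTR by cardiac biopsy; or" "Cardiac Scintigraphy Grade 2 or above". The same section treats Grade 0 as negative. SAP 6.1.1.1, which governs the secondary analyses, also admits Grade 1 participants diagnosed by a method other than cardiac biopsy.

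**What the SAP says on genotype.** Sections 2.1 and 3.2 and the genotype bullet in 6.2 all restrict it to diagnosed participants, and the bullet limits it to numbers and percentages. Two places point the other way. The sentence opening 6.2 says that the endpoints listed below it are compared between participants with and without ATTR-CM, and genotype is on that list. Appendix 1 ticks the column for ATTR-CM vs HFpEF Participants on the row "Proportion of participants with WT and hereditary forms among participants diagnosed with ATTR-CM as defined in Section 6.1.1.1", in the All Enrolled set.

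**The concern.** A comparison needs the variable measured in both groups. Here the laboratory rule and the diagnosis rule together leave it unmeasured in almost all of one group. A programmer working from Protocol 9, or from the Appendix 1 tick, would fill a column for HFpEF without ATTR-CM from whichever non-cases happen to have a result.

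Those are people with some cardiac uptake and no confirmed diagnosis. Biopsy is not a study procedure: Protocol 8.2.1 collects confirmatory data only if such testing is done. Grade 1 participants lost to follow-up before confirmation are assumed not diagnosed (SAP 6.1 and 6.1.1.1). The group may therefore contain undetected disease. A variant frequency taken from it and labelled as HFpEF without ATTR-CM would mislead a reader about carriage in that population.

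**Working it through.** The plan gives no figure for this comparison, so the check is mainly one of logic, followed by arithmetic for scale.

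**Step 1. Cross the genotyping rule with the diagnosis rule.**

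| Scintigraphy result | Genotyped? | Group |
|---|---|---|
| Grade 2 or 3 | Yes | ATTR-CM, always |
| Grade 1, confirmed | Yes | ATTR-CM |
| Grade 1, not confirmed | Yes | Not diagnosed |
| Grade 0 | No | Not diagnosed |
| Non-evaluable | No | Separate group for several SAP summaries |

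The only row that is both genotyped and not diagnosed is unconfirmed Grade 1. Moving from the protocol definition to SAP 6.1.1.1 changes only which Grade 1 participants count as confirmed. It adds no Grade 0 result.

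**Step 2. Ask whether the Appendix 1 tick is mere table filler.** The prevalence rows show N/A in that column. The NYHA and NT-proBNP rows, which SAP 6.2 does compare between groups, carry the same tick as the genotype row. The tick therefore reads as an instruction, although it conflicts with its own row title.

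**Step 3. Size the non-case group.** Protocol 9 plans about 2000 participants at about 10% prevalence: 2000 × 0.10 = 200 cases, which matches the stated 200. Non-cases: 2000 − 200 = 1800.

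**Step 4. Size the genotyped part.** The documents give neither the Grade 1 share (g) nor the share of Grade 1 confirmed (c). Assume g from 1% to 10% and c from 0% to 50%, with the case total held at 200 and all scans evaluable.

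Genotyped non-cases = 2000 × g × (1 − c)

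- Lowest: 2000 × 0.01 × 0.50 = 10, and 10/1800 = 0.6%.
- Middle: 2000 × 0.05 × 0.75 = 75, and 75/1800 = 4.2%.
- Highest: 2000 × 0.10 × 1.00 = 200, and 200/1800 = 11.1%.

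So about 89% to 99% of non-cases would have no genotype. Step 1 does not depend on these assumptions: at any Grade 1 share, no Grade 0 participant has a result.

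**The case against.** The best reply is that the SAP has largely settled the matter. SAP 2 allows it to modify protocol plans. Its endpoint text confines genotype to diagnosed participants in 2.1, 3.2 and the 6.2 bullet, and the ticked Appendix 1 row carries that restriction in its own title. A reader might infer that the SAP as a whole specifies a variant frequency in non-cases. The documents do not support that: the SAP contradicts itself, and most of its wording is on the right side. What remains is the lead-in and the tick, which need to be brought into line.

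The protocol phrase also looks carried over. The same demographic parenthesis appears in the analyses by scintigraphy grade, NYHA class and walk-test quartile, all in diagnosed participants, where genotype is available. The comparison at issue is descriptive, and the protocol's chi-square sentence names NYHA class and symptoms, not genotype. This lowers the weight of the point but does not remove the contradiction.

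Redaction matters too. The protocol sentence runs into blacked-out text, and parts of the SAP are blacked out, so the demographic comparison may be handled somewhere the reader cannot see. That limits what can be said about the final tables, not about the visible wording.

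A reader might also infer that untested non-cases will be counted as non-carriers by dividing by all 1800. No section plans this, and SAP 5.3 rules out imputation. Nor do the documents give a figure for how many unconfirmed Grade 1 participants have the disease; one can say only that some may.

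**Conclusion.** The contradiction is real. Protocol 1.1 and 9 call for a genotype comparison that the genotyping rule cannot support, and two places in the SAP echo it against the SAP's own endpoint text. The only available comparator is unconfirmed Grade 1. On the assumed ranges this is about 10 to 200 people, or 0.6% to 11% of roughly 1800 non-cases; the ranges are for scale only.

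The reach is narrow. It would be wrong to infer damage to the main results. The primary prevalence estimate does not use genotype. The wild-type/hereditary proportion is taken among diagnosed participants, all of whom are Grade 1 to 3 and so fall under the genotyping rule, subject to local law. This is a wording correction worth making before tables are programmed.

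**What to change.** - **Protocol 1.1 and 9:** delete TTR genotype from the comparison of participants with and without ATTR-CM. Keep it in the analyses restricted to diagnosed participants.
- **SAP 6.2:** exempt the genotype bullet from the lead-in. Changing Appendix 1 alone would leave this sentence standing.
- **SAP Appendix 1:** on the wild-type/hereditary row, set the ATTR-CM vs HFpEF Participants cell to N/A.
- **Reporting:** give genotype among diagnosed participants only, and put unconfirmed Grade 1 on a separate, labelled line.

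The cost is a few wording edits and the loss of a comparison that the data cannot support. No sample or assay is added. Because SAP 2 lets the SAP modify plans outside the primary endpoint, the SAP edits can come first and the protocol wording can follow with the next amendment. If the sponsor does want the comparison, samples are already collected from all participants. Genotyping Grade 0, in full or in a random subset, would supply a comparator, but at laboratory cost and subject to consent, local law and a protocol amendment.
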